9.4 Scoring Procedure

Readers will be asked to score studies using the provided viewing software as they normally would in a clinical setting and in accordance with the AASM Manual for the Scoring of Sleep and Associated Events. Hypopneas will be scored using the recommended rule 1A criterion as laid out in the AASM (v2.6), Chapter VIII Respiratory Rules Part 1: Rules for Adults, Section D: Scoring of Hypopneas.

The same data channels will be presented to the reader in the same order and with the same labelling for every study, including:

- Abdominal respiratory effort, labelled "ABD" from either the PSG system or the TatchSleep Pro patches, as applicable
- Thorax respiratory effort, labelled "THX" from either the PSG system or the TatchSleep Pro patches as applicable
- Position channel, labelled "Position" from either the PSG system or the TatchSleep Pro patches, as applicable
- Air flow (PSG) or Tatch-Sum-Flow (TatchSleep Pro) as applicable, labelled "Flow"
- Nasal pressure (PSG) or Tatch-Sum-Pressure (TatchSleep Pro) as applicable, labelled "Pressure"
- Pulse oximetry-derived blood oxygen saturation (SpO₂), labelled "SpO₂" from either the PSG system or the TatchSleep Pro compatible pulse oximeter as applicable

On any of the respiratory signals, the reader will be able to mark:

- Apnea
- Hypopnea

On the SpO₂ signal, the reader will be able to mark:

- Relative desaturation

Additionally, the reader may mark any signal with the following signal quality indicators:

- Artifact
- Movement

9.5 AHI Calculation

The AHI will be calculated for each study following scoring. The PSG total sleep time (with device-specific total artifact time subtracted) will be used as the AHI denominator.

10. Reader Selection

Sleep technologists of any age, sex, race, ethnicity, or institutional affiliation who are qualified to read PSG night tests may participate as study readers. The selected readers must meet the following criteria:

- Be Registered Polysomnographic Technologist (RPSGT) or Registered Sleep Technologist (RST) certified
- Currently participant in the American Academy of Sleep Medicine Inter-Scorer Reliability (AASM ISR) program
- Be experienced in reading PSG night tests using at least one commercially available analysis software package
- Have provided a current curriculum vitae (CV)
- Have provided a signed Readers' Agreement

The qualified and confirmed readers will complete a training program on the analysis software to be used for the study, as well as on the study protocol prior to their participation in this study.

11. TatchSleep Pro Materials and Management

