	
2. Have a referral to the study site from a physician to complete an overnight polysomnogram test for sleep apnea detection or follow-up.
 
3. Be willing and able to wear two TatchSleep Pro patches and an FDA-cleared pulse oximeter in conjunction with a polysomnogram, for a single night.
 
4. Be able and voluntarily willing to sign a written informed consent form prior to the initiation of any study procedures. Adult patients unable to provide written informed consent on their own behalf will not be eligible for the study.
 
Exclusion Criteria:
 
 1. Women who are pregnant, trying to get pregnant or who have a positive urine pregnancy test on the day of the study. 2. Women who are breast-feeding 3. Significant cardiorespiratory disease 4. Potential respiratory muscle weakness due to neuromuscular condition 5. Awake hypoventilation or suspicion of sleep related hypoventilation 6. Chronic opioid medication use 7. History of stroke 8. History of severe insomnia 9. Any known health condition that, in the opinion of the Investigator, would exclude the patient from participating in the study.
Number of Patients:	Approximately 50
Data Elements:	
The following data elements will be collected:
 
 • Height, weight, age, gender, skin tone (according to the Fitzpatrick scale), presence or lack of body hair under TatchSleep Pro patches. • TatchSleep Pro data (including patient movement, sleep position, pulse oximetry, and respiration) • PSG data (including sleep stages, total sleep time, sleep position, pulse oximetry, heart rate, and respiration). • Adverse events
Statistical Methods:	
Accuracy of the TatchSleep Pro device will be demonstrated by comparing the Pearson correlation of TatchSleep Pro and PSG AHI to a performance goal. The performance goal is based on a meta-analysis of FDA-cleared similar devices. Fisher's transformation and one-sided Z-test will be used to test the hypotheses with a significance level of 0.025. The upper and lower 95% Bland-Altman limits of agreement will be calculated and statistically compared using a Wald test to performance goals based on a meta-analysis of FDA-cleared similar devices.

	Deming regression will also be presented. The inter-rater reliability of TatchSleep Pro AHIs will be calculated.
--	--

CONFIDENTIAL

2. Background and Rationale

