Obstructive sleep apnea (OSA) is characterized by reduced breathing and breathing cessation during sleep. It is a highly prevalent condition that affects an estimated 14% of adult men and 5% of adult women aged 30 to 70 [1]. OSA is associated with more than 30 chronic conditions, such as increased risk of cardiovascular complications, and daytime fatigue and sleepiness. While the clinical gold standard for the diagnosis of OSA is polysomnography, these in-laboratory tests are expensive, time consuming, and labor intensive.

In recent years there is a growing use of home sleep tests (HSTs) as a more convenient and cost-effective alternative to diagnose sleep disorders. Nevertheless, HSTs currently on the market contain several complex wires and tubes that may make it difficult for patients to use on their own. In addition, patients report that they can be intrusive and uncomfortable. These factors lead to unreliable data collection and ineffective diagnosis of OSA [2].

TatchSleep Pro is a system comprised of flexible, thin, and wireless adhesive patches, coupled with an FDA-cleared compatible pulse oximeter, for the detection of sleep apnea. The wearable sensors detect various physiological parameters related to sleep quality, including respiration, SpO₂, and sleep position, and transmits data wirelessly to a smartphone app in real time. The data recorded by the patches is relayed to remote secure storage, from where it is downloaded to a local PC. The study output file is prepared by Tatch staff for review by a qualified sleep scorer.

The TatchSleep Pro device was bench-tested against industry standard polysomnography devices to compare the different sensors. Using its proprietary technology, TatchSleep Pro showed excellent accuracy and sensitivity in measuring respiration and sleep position. Previous feasibility testing was conducted on approximately 30 patients to evaluate the user experience and effectiveness in using the patch technology.

As a low-cost and user-friendly home sleep testing system, TatchSleep Pro has the potential to improve the detection of OSA while reducing the burden on patients and providers caused by complicated and invasive sleep kits.

In the current study, TatchSleep Pro will be evaluated as a tool to assist physicians in determining the overall Apnea Hypopnea Index (AHI) of a patient. Tatch, Inc. has partnered with the multiple clinical sites for this study.

3. Study Objectives

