3.1 Primary Objective

- Demonstrate clinical agreement between TatchSleep Pro and PSG signals by comparing the Apnea Hypopnea Index (AHI) values derived from a clinical reading of each set of signals.

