8.5 TatchSleep Pro Administration

The TatchSleep Pro will be connected to the patient by the investigator or designee according to the instructions in the provided User Manual. The investigator or designee will follow the instructions in the pre-loaded smartphone app to place the patches on the patient's chest and abdomen, as well as the pulse oximeter on the patient's finger. Once the sensors are set up and the participant is ready for bed, the investigator or designee will start the data collection using the app.

Details about TatchSleep Pro management can be found in Protocol Section 11.

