8.7 Onsite PSG Study Scoring and Export

After the completion of data collection from patients, de-identified PSG signals will be exported from the PSG at the clinical site including, at a minimum, manual position annotations and sleep staging scored according to the standard of care by a sleep technologist at the study site. Raw PSG sleep data (including, at a minimum, respiratory effort, respiratory pressure, respiratory flow and oxygen saturation signals) will be extracted and presented to qualified readers as described below.

9. Study Scoring

Once study enrollment and all sleep tests are complete, and all exported PSG data (with position annotations and sleep staging) has been received by the Sponsor, the primary reader will score all sleep study recordings made simultaneously with TatchSleep Pro and the PSG device from all sites. The primary reader will be blinded to the device used to collect the data under review as well as any information which may allow them to link the two studies from each patient. The AHI will be calculated for each study, and the set of AHIs derived from TatchSleep Pro data will be compared with those derived from PSG data using Pearson correlation to demonstrate accuracy (see Protocol Section 11 for more details). At least one and up to two additional readers (secondary readers) will each score all sleep study recordings made using the TatchSleep Pro device at all sites. The AHIs derived from these scorings will be used to calculate the inter-rater reliability for the TatchSleep Pro device signals.

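### The TatchSleep AHI is divided by PSG sleep time and no PSG-free AHI is planned, so success shows agreement only given PSG-defined sleep time

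*Combined protocol and SAP*

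**What the plan says.** Section 9.5 states: "The PSG total sleep time (with device-specific total artifact time subtracted) will be used as the AHI denominator". The rule covers every study, so the TatchSleep AHI is also divided by PSG sleep time. The two denominators can differ only through each system's own artifact time. The staging behind that sleep time comes from the PSG export, described in 8.7 as "manual position annotations and sleep staging scored according to the standard of care by a sleep technologist at the study site".

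The synopsis, under Data Elements, lists "PSG data (including sleep stages, total sleep time, sleep position, pulse oximetry, heart rate, and respiration" for PSG but "TatchSleep Pro data (including patient movement, sleep position, pulse oximetry, and respiration" for the device. Sleep stages and total sleep time appear only in the first list.

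The primary objective in 3.1 is to "Demonstrate clinical agreement between TatchSleep Pro and PSG signals" by comparing AHI values. Section 2 describes a wider purpose for this study: "TatchSleep Pro will be evaluated as a tool to assist physicians in determining the overall Apnea Hypopnea Index (AHI) of a patient". It also says: "As a low-cost and user-friendly home sleep testing system, TatchSleep Pro has the potential to improve the detection of OSA". Section 9.2 cites the AASM home-testing rules, but only for deducting invalid time.

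None of the endpoints and analyses in sections 4, 14.5 and 14.6 uses recording time or a sleep time derived from the device. Section 14.1 leaves further details to the SAP.

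**The concern.** A physician using the system that section 2 describes would have no PSG and therefore no PSG sleep time. That physician's AHI carries two sources of error: which events are marked, and how much sleep they are divided by. The plan measures the first and supplies the second from the reference method. The correlation, limits of agreement (LOA), Deming regression, reader reliability and severity-class agreement are all computed with sleep time taken from PSG.

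What is at stake is the reach of the conclusion. Success would support agreement of event scoring and signal-validity marking once sleep time is known from PSG. It would not show how well an AHI from TatchSleep alone agrees with PSG AHI.

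**Working it through.** **1. The plan's own figures (14.5, 14.8).** Inputs: n = 46, planning r = 0.98, performance goal 0.862, one-sided 0.025. On the Fisher scale, atanh(0.98) = 2.298 and atanh(0.862) = 1.301. Power = Φ((2.298 − 1.301)·√43 − 1.96) = 99.9998%, consistent with the stated 99.99%. The smallest observed r that passes is tanh(1.301 + 1.96/√43) = 0.922. The plan's power is not in question.

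**2. What can enter the comparison.** Let T be PSG total sleep time, E the events and A the artifact time. TatchSleep AHI = E_T/(T − A_T) and PSG AHI = E_P/(T − A_P). If the artifact times are equal, T cancels from the ratio and only the event counts remain. If they differ, T is still the same number on both sides. A device user's error in T has no route into any planned result.

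**3. AHI without PSG sleep time.** The documents do not say which denominator such a user would apply. Assume recording time R, the same events and no artifact. The device-only AHI is then the 9.5 value times s = T/R. Section 9.1 scores only recordings that cover the PSG sleep period, so s is at most 1. The documents give no sleep efficiency; the values below are assumed.

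| s | AHI 15 reads | AHI 30 reads |
|---|---|---|
| 0.9 | 13.5 | 27 |
| 0.8 | 12.0 | 24 |
| 0.7 | 10.5 | 21 |

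Artifact changes this little. With 30 minutes of artifact during sleep in an assumed 480-minute recording, the factor is (480s − 30)/450 = 0.893/0.787/0.680.

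**4. Events marked in wake.** The channels listed in 9.4 include no sleep stage (the list is open-ended), so device-only scoring could add events during wake. If these occur at w times the sleep rate, the factor is s + (1 − s)w. At w = 0.5 it is 0.95/0.90/0.85, that is 5/10/15% lower. At w = 1 there is no change.

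**5. Correlation.** Let D be the device AHI under 9.5, and let efficiency have mean m and SD v between patients, independent of AHI. The covariance with PSG AHI is multiplied by m, and the variance of the device-only AHI is m²·SD(D)² + v²·(SD(D)² + mean(D)²). Hence

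r′ = r / √(1 + (v/m)²(1 + k²)), where k = mean(D)/SD(D).

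With r = 0.98 and k assumed:

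| m, v | (v/m)² | r′ at k = 1.0 | r′ at k = 1.5 |
|---|---|---|---|
| 0.90, 0.05 | 0.0031 | 0.977 | 0.975 |
| 0.80, 0.10 | 0.0156 | 0.965 | 0.956 |
| 0.70, 0.15 | 0.0459 | 0.938 | 0.914 |

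In the last row r′ is below 0.922 when k exceeds √(((0.98/0.922)² − 1)/0.0459 − 1) = 1.35. In the middle row k would have to exceed 2.70. A simulation with mean AHI 22 (gamma) and no device bias gave r = 0.981/0.967/0.937 with measurement SD 3.5. With SD 7.0, where the PSG denominator itself gives 0.944, it gave 0.941/0.928/0.899.

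**6. Limits of agreement.** Illustration, not fitted to the pilot: PSG AHI mean 20, SD 18, no device bias, error SD 3.5. Then SD(D) = √(18² + 3.5²) = 18.34 and Cov(D, PSG) = 18² = 324. The variance of the difference is m²·18.34² + v²(18.34² + 20²) + 324 − 2m·324. The mean difference is 20(m − 1) and the LOA are that ± 1.96 SD.

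| m, v | mean difference | SD | LOA |
|---|---|---|---|
| 0.90, 0.05 | −2 | 3.87 | −9.6 to 5.6 |
| 0.80, 0.10 | −4 | 5.31 | −14.4 to 6.4 |
| 0.70, 0.15 | −6 | 7.19 | −20.1 to 8.1 |

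The simulation in step 5 gave at its widest −23.5 to 10.9 (SD 7.0, efficiency 0.70/0.15). All of these lie within −30.6 to 28.4. The direction depends on the starting bias. The pilot LOA in 14.8 centre on (10.6 − 3.2)/2 = 3.7, and the text does not say which system reads higher. If the device reads higher, a recording-time denominator moves it towards PSG; if lower, away from it.

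**The case against.** The strongest reply is that the shared sleep time is the right choice for the stated objective. Section 3.1 is about signals, and fixing sleep time isolates what the signals contribute. Section 9.5 says so openly. No endpoint claims stand-alone or home accuracy, and the home-testing phrase is background about potential. The SAP may add analyses. The device data list is open-ended, so a device sleep-time estimate is not ruled out.

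Most of this stands. The choice is defensible, the primary should stay as it is, and the size of any effect is unknown because the user's denominator and the sleep efficiency are unknown. The lower r in step 5 also follows largely from multiplying by a factor that varies between patients and is assumed independent of AHI.

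What remains is that section 2 does more than mention home use. It says that in this study the device is evaluated as an aid to determining a patient's overall AHI, and no analysis in the supplied text addresses an AHI the device can produce without PSG. That holds whichever denominator a user would apply.

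**Conclusion.** The point holds as a cheap improvement, not as an error. A successful trial would show agreement of event scoring and signal-validity marking given PSG-defined sleep time. It would leave open how well a TatchSleep-only AHI agrees with PSG AHI.

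Under a recording-time denominator with the same events, the AHI is 10/20/30% lower at efficiencies 0.9/0.8/0.7, before any offset from events marked in wake. The net effect on bias, LOA width and severity-class agreement is undetermined. Variation in efficiency that is independent of AHI lowers r. In the models shown r drops below 0.922 only at efficiency mean 0.70, SD 0.15, and the LOA stay within the goals. The 0.922 applies to the observed r, so a true value just above it does not ensure a pass, and a starting r well below 0.98 would leave less room.

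A reader might infer that 9.5 invalidates the primary comparison, that the trial would fail with a device-only AHI, or that home users would get systematically low readings. The documents support none of these. The denominator matches 3.1, the milder scenarios clear the goals, and neither the user's denominator nor the rate of events marked in wake is given.

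**What to change.** Keep the primary endpoint, its test and the sample size unchanged.

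- In 9.5 and 14.6, before scoring starts, pre-specify a supplementary TatchSleep AHI from device data only: all events marked in the TatchSleep recording, divided by valid TatchSleep recording time, or by the device's own sleep-time estimate if it has one.
- Report its correlation, LOA and severity-class agreement with PSG AHI beside the primary results, as estimates with confidence intervals and no added success criterion.
- Word the primary conclusion as agreement given PSG-defined sleep time.

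The cost is some wording and one analysis of recordings the study makes anyway. Section 9 begins scoring only after enrolment and all sleep tests are complete, so there is time to fix the definition first. If readers are shown only part of each recording (the text does not say), the rest would need scoring. The supplementary result may look less favourable. It also only approximates home use, since the recording is made in the clinic and 8.5 provides that "the investigator or designee will start the data collection using the app".

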9.1 Scoring Population

Studies of subjects whose TatchSleep Pro recording does not encompass the sleep period indicated by PSG will not be scored [3]. Studies from all other participants who are enrolled, meet all the inclusion criteria and none of the exclusion criteria, and whose PSG study has >4 hours of sleep duration will be scored [3].

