9.2 Reasons for Data Exclusion

Time periods marked by the reader as "Movement" or "Artifact" (collectively referred to as "invalid") in a study will not contribute to the total sleep time for the purpose of calculating AHI for that study (per guidelines in the American Academy of Sleep Medicine (AASM) Manual for the Scoring of Sleep and Associated Events section IX: Home Sleep Apnea Testing Rules for Adults). Percentage of "invalid" time will be reported for each study.

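### The AHI rule in 9.5 conflicts with 9.2 and does not confine events or invalid time to PSG-scored sleep, so it can create a device difference when the events are the same

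*Combined protocol and SAP*

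**What the plan says.** **Denominator.** Section 9.5 gives the rule: "The PSG total sleep time (with device-specific total artifact time subtracted) will be used as the AHI denominator". Section 9.2 covers periods the reader marks as Movement or Artifact, calls both invalid, and says they "will not contribute to the total sleep time for the purpose of calculating AHI for that study". Section 9.5 names artifact only.

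**Numerator.** Section 9.5 does not define it. Section 9.4 introduces the event marks with "On any of the respiratory signals, the reader will be able to mark" (apnea, hypopnea), and the quality marks with "the reader may mark any signal with the following signal quality indicators" (artifact, movement). Neither is tied to sleep. Scoring is to be "in accordance with the AASM Manual for the Scoring of Sleep and Associated Events", with no study rule for wake epochs.

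**What the reader sees.** Section 9.4: "The same data channels will be presented to the reader in the same order and with the same labelling for every study, including" abdominal and thoracic effort, position, flow, pressure and SpO2. EEG and sleep stages are not on the list.

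**Staging and coverage.** Section 8.7 exports "manual position annotations and sleep staging scored according to the standard of care by a sleep technologist at the study site", so epoch-level sleep information exists. Under 8.5, collection starts once the sensors are on and the participant is about to go to bed. Under 9.1, the studies of any subject whose "TatchSleep Pro recording does not encompass the sleep period indicated by PSG will not be scored". Nothing trims the recording to the sleep period.

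**Use.** Section 14.5 bases both co-primary objectives (Pearson correlation and Bland-Altman limits) on this AHI. So do the Deming regression, inter-rater ICC and severity-class analyses in 14.6.

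**The concern.** PSG total sleep time excludes wake by definition. Artifact marked during wake was never part of it, so subtracting total artifact time removes validly recorded sleep from the denominator. An event marked during wake has the opposite mismatch: it is counted, but the time in which it occurred is not.

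Both recordings contain some wake by design, and the reader, on the channels listed, has no staging with which to leave it out. The subtraction is made separately for each device, and the two systems use different respiratory sensors, so the amount of wake artifact need not match. A TatchSleep Pro-PSG difference could then arise from the formula alone and pass into both co-primary endpoints.

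Separately, two programmers given the same marks could compute different AHIs, one following 9.2 and the other 9.5.

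**Working it through.** **The plan's own figures.** The AHI rule carries no stated figure. The power statements in 14.8 reproduce and do not depend on the rule:
- Correlation: Phi[(atanh 0.98 - atanh 0.862) x sqrt(46 - 3) - 1.96] = 99.9998% (stated 99.99%).
- SD for a limit of agreement: sqrt(3) x 7.0 = 12.12 (stated 12.1).

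**Denominator.** Let T be PSG total sleep time, S the artifact hours inside PSG sleep and W the artifact hours outside it, all for one device.
- Overlap-only rule (9.2): AHI = events / (T - S).
- Literal rule (9.5): AHI = events / (T - S - W).
- Ratio, literal to overlap-only: (T - S) / (T - S - W).

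The documents give no value for W, so the values below are assumptions. With T = 6 h and S = 0:

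| W on one device | Ratio | AHI 15 becomes | AHI 30 becomes |
|---|---|---|---|
| 0 h | 1.00 | 15.0 | 30.0 |
| 0.25 h | 6/5.75 = 1.04 | 15.7 | 31.3 |
| 0.5 h | 6/5.5 = 1.09 | 16.4 | 32.7 |
| 1 h | 6/5 = 1.20 | 18.0 | 36.0 |

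Over T from 4.5 to 7 h, S from 0 to 0.5 h and W from 0.25 to 1 h, the inflation runs from 4% to 33%. At W = 0 the two rules agree.

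**Numerator.** Wake events add (number of wake events) / denominator. With 6 h, 6 events add 6/6 = 1 event/hour. Over T from 4.5 to 7 h, 5 to 20 events add 0.7 to 4.4 events/hour. This error is additive; only the denominator error is proportional to AHI. For scale, the pilot SD of differences in 14.8 is 3.5 and the planning SD is 7.0.

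**The 4-hour rule does not bound the error.** Section 14.2 requires 4 h of valid oximetry and flow in the recording, not in sleep. Take an assumed extreme: an 8 h recording with T = 4.5 h and W = 3 h. Valid data are 8 - 3 = 5 h, so the subject stays in, but the literal denominator is 4.5 - 3 = 1.5 h and the AHI is tripled.

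**Effect on the endpoints, by illustrative simulation.** All inputs are assumed: a gamma-distributed AHI (shape 1.3, scale 15, capped at 90), a normal difference with SD 7 and device AHI floored at 0, T uniform on 4.5 to 7.5 h, and exponential wake artifact capped at 1.5 h. Differences are TatchSleep Pro minus PSG.

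| Mean W, PSG / TatchSleep Pro (before cap) | Bias | SD | Limits of agreement | r |
|---|---|---|---|---|
| 0 / 0 h | 0.41 | 6.51 | -12.4 to 13.2 | 0.929 |
| 0.25 / 0.25 h | 0.43 | 7.09 | -13.5 to 14.3 | 0.924 |
| 0.1 / 0.5 h | 1.97 | 7.65 | -13.0 to 17.0 | 0.920 |
| 0.1 / 1.0 h | 3.38 | 8.62 | -13.5 to 20.3 | 0.915 |

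In the last row the standard error of a limit with 46 subjects is sqrt(3) x 8.62 / sqrt(46) = 2.20. The upper limit plus 1.96 standard errors is 20.3 + 4.3 = 24.6, still below 28.4. The lower is -13.5 - 4.3 = -17.8, well above -30.6.

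**The case against.** The strongest reply is that 9.2 already settles the denominator. Only time inside total sleep time can cease to contribute to it, so wake artifact is never subtracted and 9.5 is shorthand. Movement is also covered, because 9.2 defines both marks as invalid. This is a fair reading of 9.2, and for artifact it makes the matter a conflict between two sections, not a settled error. But 9.5 is the section that states the calculation, and it says total artifact time. Section 9.2 also leaves the numerator unrestricted.

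Second, the channel list is introduced as open, staging is exported, and AASM scoring is required, so readers might be shown sleep stages or marks might be filtered later. That is possible, and the documents do not say otherwise. They do not say so either. Section 14.1 defers other details to a SAP, but the text supplied contains no such rule. Staging would also be hard to display under 9.3: shown on PSG studies only, it would reveal the device, and shown identically on both, it could link a subject's two records.

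Third, the recordings are simultaneous, so movement-related marks may fall on both devices and partly cancel. This stands for the mean: equal average wake artifact moved the simulated bias only from 0.41 to 0.43. It does widen the limits slightly, because the amounts vary between patients.

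A reader might infer that AHI will be distorted, or that one device will be favoured. The documents support neither. Distortion needs marks outside PSG sleep, whose amount is not given for either device, so size and direction are unknown.

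**Conclusion.** Sections 9.2 and 9.5 conflict on what is removed from the denominator, and no stated rule confines counted events to PSG-scored sleep. Followed literally, 9.5 can give a wrong AHI, by an amount that can differ between the devices. The size is conditional: 0% to 20% for 0 to 1 h of wake artifact on one device with 6 h of sleep, plus about 1 event/hour for every 6 wake events. Both are assumptions, and zero is within the range.

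A changed trial verdict is not shown. In every simulated case the limits of agreement stayed inside 28.4 and -30.6. For the correlation, a reader might notice that with 46 subjects the observed r must exceed tanh(atanh 0.862 + 1.96/sqrt(43)) = tanh(1.301 + 0.299) = 0.922, and that the simulated r falls from 0.929 to 0.920. That is not evidence that the test would fail. The starting value of 0.929 comes from the assumed AHI spread and SD of 7, and the plan assumes 0.98. Inflation by a constant proportion would leave Pearson r unchanged; only its variation between patients lowers it.

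The point should be settled before scoring, because the rule feeds both co-primary endpoints and a choice between the two readings should not be made with results in view.

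**What to change.** Rewrite 9.5 so that it agrees with 9.2:
- **Numerator:** apneas and hypopneas within PSG-scored sleep and outside periods invalid on that device, with a prespecified rule for events that cross a sleep-wake boundary.
- **Denominator:** PSG total sleep time minus only the Movement or Artifact time on that device that overlaps PSG-scored sleep.
- **Several channels:** overlapping marks on more than one signal are counted once, so that the same minutes are not subtracted twice.

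Apply the rule by program after blinded scoring, using the staging exported under 8.7. Readers see nothing new, so blinding is unchanged, as are the sample size and planned power.

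The cost is the wording, a programming rule, and time alignment of the TatchSleep Pro recording with the PSG staging. No alignment procedure is described, so one should be added; 9.1 already requires the recording to be compared with the PSG sleep period.
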